Official Title: Early neurological deterioration in recent small subcortical infarction: a multicenter prospective study

NCT number: not available

Date: December 25, 2022

Background and objectives

Recent small subcortical infarction (RSSI) is defined as a small deep infarction in the territory of a perforating artery with maximum axial diameters (MAD) of less than 20 mm. Although RSSI is generally considered to be of a relatively favorable prognosis, about 13.5% to 43% of RSSI patients experience early neurological deterioration (END) in the acute phase, which often bring adverse effects on long-term outcomes. Although a number of risk factors for END have been identified previously, however, the risk factors of END and the underlying etiological mechanism are still ambiguous, and also the relevant intervention measures lack sufficient evidences, which is a thorny problem that clinicians have to face.

In this multicenter, large-sample prospective registry study, the primary objective is to investigate the natural course of END in patients with RSSI. Exploring the risk factors and potential mechanism of its development, and trying to establish a comprehensive predictive model for END that integrates multi-dimensional information including clinical symptom, demographic data, biochemical biomarker and image data, and so as to provide a valuable tool for clinical evaluation and early management. Secondary objective is to figure the long term outcome of the patients with RSSI and its risk factors.

Methods

Study design

This study is a multicenter, consecutive, prospective, observational, cohort study recruiting RSSI patients within 72 hours after symptom onset. This study was approved by the Ethics Committee of The First Affiliated Hospital of Zhengzhou University. The anticipated duration of the study will be about 2 years from June 1, 2022 to June 1, 2024.

Study population

Inclusion criteria.

1. Age \geq 18 years;
2. Time from the last seen normal to enrollment \leq 72 h;
3. Completion of brain MRI (T1/T2/Flair/DWI/ADC sequences). The lesion belonged to the territory of the penetrating artery (lenticulostriate area and pons) on the DWI sequence and at least one of the vascular examinations such as MRA, CTA or DSA was completed.

Exclusion criteria.

1. Patients with low imaging quality affecting the evaluation of the results;

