2. Intracranial hemorrhagic diseases, vascular malformations, aneurysms, brain abscesses, malignant space occupying lesions or other non-ischemic intracranial lesions observed by baseline head imaging;

3. Patients with combined malignancy, hematological disease and other systemic diseases with possible hypercoagulable state;
4. mRS score prior to the onset of the disease was ≥ 2 points;
5. Patients with symptom progression or TIA before completion of cranial MRI after admission;
6. Received or plan to receive acute endovascular treatment after onset of the disease;
7. Pregnant or lactating women;
8. Participation in another ongoing study;
9. Those who refused to participate in the study.

Data collection

RSSI patients within 72 hours of stroke onset were prospectively and consecutively enrolled from June 2022 to June 2023. After enrollment, Clinical data will be collected using an online electronic case report Form (e-CRF) at baseline and follow-up. Baseline data including demographic, first blood pressure, past and family history, past medications use, pre-stroke modified Rankin Scale score (mRS), assessment of mRS and NIHSS score on admission were recorded. After admission, NIHSS score was evaluated twice a day by two certified physicians, who were blinded to the study. laboratory tests including routine blood/biochemistry/renal function, etc.) Transthoracic echocardiogram, 24-hour Holter and neuroimages data including brain MRI/MRA/CTA/DSA, etc. were all

collected. During hospitalization, the drug therapy (antiplatelet/anticoagulation, lipid-lowering, glucose lowering, antihypertensive, etc.) were also recorded. Early neurological deteriorations (END) were monitored by two certified physicians, who were blinded to the imaging, and the primary outcome of our study was the occurrence of END, which was defined as any increase of ≥ 2 points in the total NIHSS score or ≥ 1 point on the motor items of the NIHSS within 7 days of hospital admission with blind evaluation. And any new cerebrovascular events confirmed during hospitalization were recorded. By face-to face or telephone interviews, we extended the follow up to 1 year for our secondary outcome as follow. The outcomes will be assessed by the neurologists blinded to study images. The quality control of all data will be held dynamically by the central center.

Outcome measures

Primary outcome

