Any increase of ≥ 2 points in the total NIHSS score or ≥ 1 point on the motor items of the NIHSS within 7 days of hospital admission with blind evaluation.

Secondary outcome

1. percentage of patients with favorable functional recovery, defined as an mRS ≤ 1 ;
2. Percentage of patients with new vascular events, defined as any

- stroke (ischemic or hemorrhage);
3. Percentage of patients with the new clinical vascular events (ischemic stroke/ hemorrhagic stroke/ TIA/ MI/ vascular death) as a cluster and evaluated individually;
 4. Severe bleeding incidence (GUSTO definition), including fatal bleeding and symptomatic intracranial hemorrhage;
 5. Incidence of symptomatic and asymptomatic intracranial hemorrhagic events;
 6. All-cause mortality;
 7. cognitive function (MOCA/MMSE score).

Sample size

In our cohort study, no specific hypothesis for the primary outcome is set, the sample size is estimated based on the number of variables, using the method recommended for registry study (10 times number of variable). The sample size is estimated as 500 , and increases to 550 for 10% loss during follow-up.

Statistical analysis

Categorical variables will be presented as frequencies and percentages, Continuous variables with non-normal distributions will be shown as median and interquartile range (IQR), while continuous variables with normal distributions as mean and 95% confidence interval (CI). For the statistical significance analysis of different

groups and outcomes, Pearson χ^2 or Fisher's exact test, Wilcoxon tests, and t-tests will be used, where appropriate, with statistical uncertainty expressed by means of 95% CI. Cox proportional hazards model, Logistic regression model, and Poisson regression model will be used to assess the association between outcomes and predictors, where appropriate. All associated variables in the univariate analysis that reached $P < 0.10$ were included in the multinomial logistic analysis as candidate variables and then removed by a forward conditional selection. A two-sided $P < 0.05$ was considered statistically significant. The good prognosis is defined as 0–2 mRS score, and poor prognosis as 3–6 mRS score on 12 mon. All analysis will be performed using SPSS 26.0 (SPSS, Inc., Chicago, IL).

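### The protocol aims at a prediction tool for early neurological deterioration, but its only model-building rule is P<0.10 screening plus forward selection, with no validation or performance measure

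*Combined protocol and SAP*

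**What the plan says.** The Background and objectives section describes the authors as "trying to establish a comprehensive predictive model for END that integrates multi-dimensional information", "so as to provide a valuable tool for clinical evaluation and early management". It gives the expected frequency: "about 13.5% to 43% of RSSI patients experience early neurological deterioration (END) in the acute phase". It also notes that "a number of risk factors for END have been identified previously", while calling the risk factors still unclear.

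The Statistical analysis section lists Cox, logistic and Poisson regression for studying associations between predictors and outcomes. Its one rule for building a multivariable model is that variables reaching P<0.10 univariately "were included in the multinomial logistic analysis as candidate variables and then removed by a forward conditional selection". The next sentence sets a general two-sided 0.05 significance level. No entry or removal threshold is stated for the selection, and the sentence does not say which outcome it serves.

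The Sample size section takes ten patients per variable to reach 500, which "increases to 550 for 10% loss during follow-up". END is assessed "within 7 days of hospital admission with blind evaluation". The longer follow-up is for other endpoints: "we extended the follow up to 1 year for our secondary outcome".

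No section mentions a bootstrap, cross-validation, a split or external sample, shrinkage, an AUC or C-statistic, or calibration.

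**The concern.** A tool offered for patient management is judged by how well it predicts in patients who did not contribute to it. Under the natural reading of the plan, the same patients serve to choose the predictors and to estimate their coefficients, and nothing corrects for that double use. Three consequences follow: noise variables tend to enter, retained coefficients tend to be too large because selection favours overestimates, and any accuracy computed in the development data is too high. Users of the tool would have no figure for its performance in new patients.

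If the rule is not meant for the END model, a stated aim has no analysis plan at all. Either way the section needs completing.

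A wording point only: END is yes or no, so the model is binary (multivariable) logistic, not multinomial.

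**Working it through.** **The plan's own figures.** 10 × 50 = 500, so about 50 variables are implied; the plan does not state the number. 500 × 1.10 = 550 reproduces the stated total (500/0.90 would give 556).

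**Expected END events**, using the protocol's range of 13.5% to 43%:
- n = 550: 550 × 0.135 = 74 and 550 × 0.43 = 237. With 50 candidates, 74/50 = 1.5 and 237/50 = 4.7 events each.
- n = 500: 500 × 0.135 = 68 and 500 × 0.43 = 215.

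The main case is n = 550, because the 10% allowance is for loss during follow-up whereas END is observed within 7 days of admission.

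**Chance selection.** With 50 independent pure-noise candidates, 50 × 0.10 = 5 are expected to pass the screen. The chance that at least one reaches P<0.05 is 1 − 0.95^50 = 92%.

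**Simulation of the rule.** The following are assumptions, not plan figures: five true predictors, independent normal predictors, the stated odds ratios per SD, 15 to 50 candidates, entry at P<0.05 and removal at P>0.10. The 0.05 entry level follows one reading of the general significance level. Each cell has 1,000 cohorts, evaluated in 5,000 new patients. Optimism is apparent AUC minus new-patient AUC; its Monte Carlo standard error is at most 0.0013.

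Results at n = 550:

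| Candidates | OR per SD | END rate | Apparent AUC | New-patient AUC | Optimism | Calibration slope |
|---|---|---|---|---|---|---|
| 50 | 1.4 | 13.5% | 0.731 | 0.641 | 0.090 | 0.57 |
| 50 | 1.4 | 43% | 0.713 | 0.669 | 0.044 | 0.77 |
| 50 | 1.8 | 13.5% | 0.824 | 0.776 | 0.048 | 0.79 |
| 50 | 1.8 | 43% | 0.801 | 0.777 | 0.024 | 0.89 |
| 25 | 1.4 | 13.5% | 0.715 | 0.652 | 0.063 | 0.68 |
| 25 | 1.4 | 43% | 0.704 | 0.676 | 0.028 | 0.85 |
| 25 | 1.8 | 13.5% | 0.814 | 0.786 | 0.028 | 0.87 |
| 25 | 1.8 | 43% | 0.796 | 0.782 | 0.014 | 0.93 |
| 15 | 1.4 | 13.5% | 0.707 | 0.658 | 0.049 | 0.74 |
| 15 | 1.4 | 43% | 0.700 | 0.680 | 0.020 | 0.89 |
| 15 | 1.8 | 13.5% | 0.809 | 0.789 | 0.020 | 0.91 |
| 15 | 1.8 | 43% | 0.795 | 0.784 | 0.011 | 0.94 |

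At least one noise predictor was kept in about 35% of models with 15 candidates at OR 1.8, and in 87% to 90% with 50 candidates at OR 1.4. Retained true coefficients were 2% to 23% too large.

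**Sensitivity** (each pair is END 13.5% then 43%):
- n = 500, 50 candidates at OR 1.4: optimism 0.097 and 0.049, slopes 0.54 and 0.74.
- n = 500, 15 candidates at OR 1.8: optimism 0.025 and 0.012, slopes 0.89 and 0.94.
- n = 550, predictors correlated at 0.3, 50 candidates at OR 1.4: optimism 0.786 − 0.732 = 0.054 and 0.774 − 0.739 = 0.035.
- Same correlation, 15 candidates at OR 1.8: optimism 0.880 − 0.864 = 0.016 and 0.863 − 0.854 = 0.009.

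Optimism was positive in all 28 cells run. A separately written simulation at n = 500 with 50 candidates and other effect sizes also found it in every scenario. With no true predictors at all, apparent AUC was 0.628 and 0.592 against 0.500 in new patients.

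**Does bootstrap correction work here?** At n = 550, 100 cohorts with 100 bootstraps each, repeating screening and selection:

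| Candidates, OR | END rate | Apparent AUC | Corrected AUC | New-patient AUC | Slope before shrinkage | Slope after |
|---|---|---|---|---|---|---|
| 50, 1.4 | 13.5% | 0.735 | 0.640 | 0.643 | 0.57 | 0.95 |
| 50, 1.4 | 43% | 0.712 | 0.651 | 0.668 | 0.77 | 1.10 |
| 15, 1.8 | 13.5% | 0.810 | 0.781 | 0.787 | 0.89 | 1.03 |
| 15, 1.8 | 43% | 0.792 | 0.776 | 0.783 | 0.95 | 1.03 |

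The corrected AUC was 0.003 to 0.017 below the new-patient value, closer to it than the apparent AUC in all four cells.

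**The case against.** The strongest reply is that the link is inferred. The selection sentence names no outcome, the regressions are described as studies of association, and the rule could equally serve the 12-month mRS prognosis defined shortly afterwards. The primary objective is the natural course of END, the model is something the authors hope to establish, and no accuracy figure is promised. This stands as a limit on certainty, so the conclusion is conditional. It does not supply the missing plan: a stated aim still has no other modelling rule and no performance measure.

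The size also rests on inputs the documents do not give, and it varies about tenfold. The mild case changes both candidate number and signal strength relative to the severe one, and is of little practical importance. The 28 cells share the same selection rule, number of true predictors and similar n, so they are not independent confirmations. The correlated cells hold odds ratios fixed, which raises total signal (new-patient AUC 0.641 becomes 0.732 in the severe 13.5% cell), so they do not isolate correlation. All of this stands, and the figures should be read as illustrations.

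Finally, the remedy is imperfect. At 43% END with 15 candidates the bootstrap removes 0.792 − 0.776 = 0.016 where true optimism is 0.792 − 0.783 = 0.009. One shrunken slope overshoots to 1.10. Shrinkage also leaves noise predictors in a stepwise model. These are reasons to prefer penalisation of a pre-specified list, not to go without validation.

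**Conclusion.** The concern holds. The absence of any validation, shrinkage or performance measure for the intended END tool is certain from the text. That the P<0.10 and forward-selection rule would build the tool is the natural reading, but an inference.

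Under that reading, AUC optimism ranges from about 0.01 (few candidates, strong signal, frequent END) to about 0.10 (50 candidates, weak signal, END at 13.5%, 500 analysed), with calibration slopes from 0.94 down to 0.54. The direction is robust across the settings tried; the size depends on the assumed predictors, effects and thresholds. Without validation, nobody could tell where in that range the study falls. END incidence and the secondary outcome percentages are not affected. This should be fixed before analysis.

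**What to change.** Add a short prediction-model subsection to the Statistical analysis section:

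1. State that the END model is a binary (multivariable) logistic regression.
2. Pre-specify the candidates, starting from risk factors already reported. The protocol lists none, so the investigators must name them. Limit the list by expected events: as an illustration, the plan's own factor of ten applied to events at n = 550 gives 74/10, about 7, to 237/10, about 23, candidates. The low end strains the aim of combining clinical, demographic, biomarker and imaging data, so the choice should be justified.
3. Preferably fit that list with penalisation and no univariate screen. Alternatively keep the stepwise rule, state its entry and removal thresholds, and shrink its coefficients by the bootstrap-corrected slope.
4. In either case repeat every modelling step within each bootstrap sample, and report the optimism-corrected C-statistic, calibration slope and calibration plot.

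The cost is SAP wording and modest programming, with no new patients or data. If the work cannot be done in SPSS 26.0, the software statement must be amended too. The reported AUC will be lower, by about 0.01 to 0.10 depending on candidate number and signal, and the corrected value may be slightly pessimistic.

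### The variable-selection rule does not keep END out of the 12-month mRS model; if END enters, baseline factors acting through it tend to be dropped or attenuated

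*Combined protocol and SAP*

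**What the plan says.** Background and objectives sets the long-term aim: "Secondary objective is to figure the long term outcome of the patients with RSSI and its risk factors". The same section says that RSSI patients may have END, "which often bring adverse effects on long-term outcomes", and gives its frequency: "about 13.5% to 43% of RSSI patients experience early neurological deterioration (END) in the acute phase". Finding risk factors for END belongs to the primary objective.

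Outcome measures defines END as a post-admission event: "Any increase of ≥ 2 points in the total NIHSS score or ≥ 1 point on the motor items of the NIHSS within 7 days", counted from admission.

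Statistical analysis gives a single selection rule. It starts "All associated variables in the univariate analysis that reached" P < 0.10 and says that these variables "were included in the multinomial logistic analysis as candidate variables and then removed by a forward conditional selection". It names no outcome, lists no candidates and does not restrict them by time of measurement. The same paragraph defines the 12-month split (mRS 0–2 good, 3–6 poor) and the significance level: "A two-sided $P < 0.05$ was considered statistically significant". No baseline-only model and no mediation analysis is described.

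**The concern.** The plan's own premises form a chain: baseline factors influence END, and END influences disability at 12 months. END is then an intermediate step. A regression that contains it estimates what a baseline factor adds once END status is known. That differs from whether the factor raises the risk of a poor outcome for a patient at presentation, which is the natural meaning of a risk factor for long-term outcome.

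Because END is expected to relate strongly to 12-month mRS, it would almost always pass a P < 0.10 screen and be selected. A factor identified in the primary analysis as a predictor of END could then be missing from the long-term model, and a reader could take it to be irrelevant to disability. Such a model would also mix information available at admission with information complete only at day 7, so it could not be used as an admission-time risk profile.

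**Working it through.** **Plan figures.** No stated figure bears directly on this point. The sample size is 10 × the number of variables = 500, which implies 50 variables, and 500 × 1.10 = 550 reproduces the recruitment target. I use n = 500 as the analysed number.

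**Inputs from the documents.** END rate 13.5% to 43%; entry screen P < 0.10; two-sided significance at 0.05.

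**Inputs assumed.** The documents give no effect sizes and no rate of poor 12-month mRS. The stepwise entry and removal thresholds are also not stated.

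**Step 1: one factor acting only through END.** Assume the factor is present in 30% of patients, END occurs in 35% with it and 15% without it, and poor mRS follows in 35% with END and 8% without.
- Overall END rate: 0.30 × 0.35 + 0.70 × 0.15 = 0.21, inside the plan's range.
- Odds ratio, factor to END: (0.35/0.65) / (0.15/0.85) = 3.05.
- P(poor | factor) = 0.35 × 0.35 + 0.65 × 0.08 = 0.1745.
- P(poor | no factor) = 0.15 × 0.35 + 0.85 × 0.08 = 0.1205.
- Total odds ratio = (0.1745/0.8255) / (0.1205/0.8795) = 1.54.
- Given END status the odds ratio is 1.0, because no other path was assumed.

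In 1,500 simulated studies of 500 patients, the factor was significant in about 34% without END in the logistic model and about 4.5% with it.

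**Step 2: the same factor with a direct odds ratio of 2.** Doubling the odds of poor mRS in patients with the factor:
- With END: odds 2 × 0.35/0.65 = 1.077, risk 0.519.
- Without END: odds 2 × 0.08/0.92 = 0.174, risk 0.148.
- P(poor | factor) = 0.35 × 0.519 + 0.65 × 0.148 = 0.278.
- Total odds ratio = (0.278/0.722) / (0.1205/0.8795) = 2.81; the model with END targets 2.0.

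The factor was significant in about 99% of simulated studies without END and 71% with it. The simulated percentages in both steps should be read to within a few points.

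**Step 3: the plan's screen and forward selection.** Steps 1 and 2 compare plain fits. A separate simulation applied the univariate P < 0.10 screen and then forward selection by likelihood ratio (entry 0.05 and removal 0.10 assumed). It used n = 500 and 1,500 samples per scenario, END rates of 13.5%, 28% and 43%, factor prevalence 40%, poor mRS 15%, odds ratio factor to END 2 or 3, and END to poor mRS 4 or 8. END, when eligible, was selected in 98% to 100% of samples.

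| Direct OR of the factor | Kept, END not a candidate | Kept, END a candidate | Lost because of END, among samples that kept it without END |
|---|---|---|---|
| 1 (acts only through END) | 10%–55% | 2%–4% | 72%–96% |
| 1.5 | 57%–92% | 30%–35% | 38%–67% |
| 2 | 90%–99% | 69%–77% | 14%–31% |

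**The case against.** The strongest reply is that the plan never says END enters the 12-month model. The selection sentence names no outcome and is attached only to the logistic analysis, while Cox and Poisson models are also mentioned. It might be meant for the END model alone. END is labelled the primary outcome, and the preceding sentence distinguishes outcomes from predictors. This stands as far as it goes: a reader might infer that the plan puts END in the model, and the documents do not support that. They show only that nothing keeps it out and that the literal rule would let it in.

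A reader might also infer that true long-term risk factors will be eliminated. That follows only for a factor acting wholly through END, where the adjusted odds ratio of 1.0 is built into the assumption. With a direct odds ratio of 2, about 70% of studies still retain the factor. Power is also limited to begin with: in Step 1 about 66% of studies miss the factor even without END.

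Three further points are fair. The objective does not define an estimand, so reading it as overall association is an interpretation. A model with END is legitimate for prognosis from day 7 or for END's own association with outcome. The univariate comparisons would still show the crude association, though unadjusted.

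None of this removes the problem. As written, the rule either leads the analyst to include END or leaves the choice until the data have been seen.

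**Conclusion.** The point holds conditionally. If the rule is applied as written to 12-month mRS, END is eligible and would very probably be selected, and the model would not give the overall association of baseline factors with 12-month outcome. Factors acting mainly through END would tend to be lost. Those with a direct effect too would usually be kept if that effect is substantial, but with a smaller coefficient (2.0 rather than 2.81 in Step 2).

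The sizes rest on assumed effect sizes and an assumed rate of poor outcome; only the END range, the P thresholds and the sample size come from the plan. It would go too far to say that the two parts of the study would contradict each other. A factor that predicts END but adds nothing once END is known is a coherent mediation pattern, provided it is reported as one.

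The primary END analysis is unaffected. This is a worthwhile correction to one secondary analysis. The argument is made for 12-month mRS and does not extend to all seven secondary outcomes, some of which are likely to be too rare to support an additional model.

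**What to change.** For 12-month mRS, add to Statistical analysis:

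- **Model A** is the analysis of long-term risk factors. Its candidates are restricted to variables known at admission or from baseline imaging.
- **Model B** contains the Model A variables plus END. It is reported separately, for the association of END with 12-month outcome or for prognosis from day 7.
- Baseline factors are not judged from Model B.

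The cost is a short addition to the SAP wording and one extra model. No new data are needed and the sample size does not change. The fix does not cure the low power for factors with a modest total effect.

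### Age and admission NIHSS can drop out of the END and 12-month mRS models on sample P values alone, because the only covariate rule is a univariate screen followed by forward selection

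*Combined protocol and SAP*

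**What the plan says.** Under Statistical analysis the plan lists the model families without naming a covariate for any of them: "Cox proportional hazards model, Logistic regression model, and Poisson regression model will be used to assess the association between outcomes and predictors, where appropriate". Covariate choice is then left to P values: variables below 0.10 on their own "were included in the multinomial logistic analysis as candidate variables and then removed by a forward conditional selection". No entry or removal level is given. The nearest figure is the general threshold: "A two-sided $P < 0.05$ was considered statistically significant".

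The two outcomes at issue are END ("the primary outcome of our study was the occurrence of END", under Data collection) and the dichotomised mRS ("The good prognosis is defined as 0–2 mRS score, and poor prognosis as 3–6 mRS score on 12 mon", under Statistical analysis). Both are binary although the selection sentence calls the analysis multinomial. It names no outcome, and no other covariate rule exists, so the natural reading is that it governs both.

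The variables needed are in hand. Data collection lists demographics at baseline and says "assessment of mRS and NIHSS score on admission were recorded". Age otherwise appears only as an inclusion criterion. No sensitivity analysis adjusted for age or severity is planned.

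**The concern.** The study is not only building a prediction tool. Background and objectives also aims at risk factors and mechanism for END, and adds: "Secondary objective is to figure the long term outcome of the patients with RSSI and its risk factors". Those are explanatory aims. For them, whether an estimate is adjusted for age and initial severity should follow from subject-matter reasoning, not from whether each variable happened to pass two significance thresholds in this sample.

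The plan collects many laboratory, cardiac and imaging variables that may be correlated with age or severity. If either is dropped, a correlated marker can carry part of its effect and be reported as a risk factor in its own right. The usual reassurance is that important predictors get selected anyway. That holds for strong predictors with many events. The question is whether it holds for moderate ones at this sample size.

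**Working it through.** **The plan's own figures.** Ten per variable and a target of 500 imply 500/10 = 50 variables; the count is not stated. Allowing for 10% loss, 500 × 1.10 = 550, as stated (500/0.90 = 556, close to it). Nothing below changes these figures.

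**Inputs from the documents.** n = 500; END rate 13.5% to 43% (Background and objectives), hence 500 × 0.135 = 67.5 to 500 × 0.43 = 215 events; screen at P < 0.10; two-sided 0.05.

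**Assumed inputs.** True odds ratio per SD of the covariate (age or NIHSS) 1.3 or 1.5; a marker with no effect of its own, correlated 0.3 or 0.5 with the covariate; entry at P < 0.05. No 12-month mRS rate is given, so the END range is used for both outcomes.

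**Step 1: chance of failing a single test.** With SE = 1/√(n p (1 − p)) and z = ln(OR)/SE, the miss probability is close to Φ(z_crit − z).

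- p = 0.135, OR 1.3: √(500 × 0.135 × 0.865) = 7.64; z = 0.262 × 7.64 = 2.00. Misses P < 0.10: Φ(1.645 − 2.00) = 36%. Misses P < 0.05: 48%.
- p = 0.43, OR 1.3: √(500 × 0.43 × 0.57) = 11.07; z = 2.90. Misses: 10% and 17%.
- OR 1.5: misses 7% and 13% at p = 0.135; 0.2% and 0.6% at p = 0.43.

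**Step 2: the whole rule, one null marker.** Simulation of the screen then forward entry (Wald tests standing in for the conditional statistic), 1,500 runs per row:

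| Outcome rate | OR per SD | Correlation | Covariate omitted | Marker kept, covariate absent | Marker kept at all | Marker significant, covariate forced |
|---|---|---|---|---|---|---|
| 13.5% | 1.3 | 0.3 | 50.5% | 4.5% | 5.9% | 5.5% |
| 13.5% | 1.3 | 0.5 | 50.1% | 5.7% | 5.7% | 5.3% |
| 13.5% | 1.5 | 0.3 | 14.2% | 1.8% | 4.0% | 5.4% |
| 13.5% | 1.5 | 0.5 | 18.2% | 4.7% | 5.2% | 4.7% |
| 43% | 1.3 | 0.3 | 21.0% | 2.7% | 4.3% | 5.3% |
| 43% | 1.3 | 0.5 | 23.6% | 6.3% | 7.0% | 5.6% |
| 43% | 1.5 | 0.3 | 0.7% | 0.1% | 2.3% | 4.7% |
| 43% | 1.5 | 0.5 | 2.1% | 1.1% | 2.8% | 4.1% |

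Repeat simulations at OR 1.3 and correlation 0.5 put omission at 51 to 55% and 22 to 24% at the two rates. The last column applies no screen to the marker. When the marker must also pass the screen, the comparison is about 5 to 6% under the plan against 2 to 3% with the covariate forced.

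In runs at OR 1.3 and correlation 0.5 where the marker was kept without the covariate, its median reported odds ratio was 1.42 (13.5% rate) and 1.28 (43%), against a true adjusted value of 1.0. Confounding alone would give roughly exp(0.5 × ln 1.3) = 1.14; the rest comes from reporting only what reached significance.

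**Step 3: five null markers, each correlated 0.5 with the covariate.** At OR 1.3, at least one null marker was kept in about 22 to 30% of studies under the plan, against 11 to 15% with the covariate forced and the rest still screened and selected. At OR 1.5 the contrast was about 24% against 13% at a 13.5% rate, and 14% against 13% at 43%.

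**The case against.** The strongest reply is that the harm is small. For one null marker the overall false-selection rate barely moves, and in some rows of the table it is lower under the plan. This stands. A reader might infer that whenever age or NIHSS is dropped, a correlated marker takes its place. The figures do not support that: at OR 1.3 and correlation 0.5 the marker was kept in 5.7/50.1 = 11% of the studies that lost the covariate at a 13.5% rate, and in 6.3/23.6 = 27% at 43%. The answer is that the plan has many candidates, and Step 3 shows that the excess accumulates across them.

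The inputs are also chosen, not documented. The plan gives no association of age or NIHSS with either outcome, no correlations and no entry level. END is observed within 7 days, so loss to follow-up may hardly apply to it. At n = 550 and OR 1.3 omission falls to about 48% and 17%, slightly lower but of the same order.

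Forcing admission NIHSS into the END model is a judgement. END is itself a rise in NIHSS, and admission severity may lie on the causal path from an imaging or biomarker factor. That stands, and the fix allows for it. It does not apply to age, and does not defeat adjusting 12-month mRS for severity.

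Three further inferences go beyond the documents. The selection sentence covers the logistic analysis only, so it cannot be read as the rule for the Cox and Poisson models. The plan does not describe retained factors as independent. It also proposes no comparison of odds ratios across outcomes, and forcing in two variables would not make the full adjustment sets equal in any case.

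**Conclusion.** The concern holds in a limited form. The plan lets age and admission NIHSS leave the END and 12-month mRS models on sample P values alone, so a retained risk factor may be reported without adjustment for them. That is a possibility the rule permits, not a certainty. It is likely for a moderate predictor at the low end of the END range, where omission is about an even chance, and it nearly disappears for a strong predictor at the high end.

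The main consequences are unadjusted or exaggerated estimates and, where several candidates are correlated with the omitted covariate, roughly twice as many studies with a spurious factor at OR 1.3. A large rise in false positives for any single marker is not supported. All percentages depend on the assumed odds ratios, correlations and entry level; the absence of any protected covariate does not. The change is worth making before analysis because it is cheap. The study does not fail without it.

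**What to change.** Add to Statistical analysis:

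> Age and admission NIHSS are kept in the multivariable logistic models of END and of 12-month mRS regardless of P value; selection applies only to the remaining candidates. For END, where admission severity may lie on the causal path for imaging or biomarker factors, estimates with and without admission NIHSS are both reported.

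The cost is about two degrees of freedom per model, against roughly 68 expected END events at the lowest quoted rate, and slightly wider confidence intervals. The END models need one extra set of estimates. The data are already collected, and the 500 and 550 targets do not change.
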